4.0 Study Endpoints

- 4.1 The study endpoint will be independent oral feeding without symptoms requiring intervention by 4 weeks or sooner.
- 4.2 The study will be ended with any safety concerns for the subject

5.0 Study Intervention/Investigational Agent

- 5.1 The intervention will be the addition of either concurrent or sequential high resolution esophageal manometry with the VFSS as well as a follow up esophageal manometry as needed. This is an accepted diagnostic tool used in infants with feeding difficulties.

6.0 Procedures Involved*

6.1 Study Design

- Study design and setting: Eligible subjects (study) will undergo diagnostic VFSS in combination with manometry, either concurrent or sequential. They will have parental choice of preferred feeding therapy. The data is from single center prospective observational study. The controls are those who had VFSS alone with provider recommendations from the same single center.
- Patient population and characteristics: (i) Study and control infants have oral feeding difficulties with symptoms requiring interventions/monitoring. (ii) They have diagnostic need for VFSS due to aerodigestive and feeding difficulties. (iii) Study subjects must have a signed informed consent from parent/legal guardian prior to manometry study. Control subjects did not require consent as they were historical controls.
- Inclusion criteria: Infants with feeding-related aerodigestive symptoms who are \leq 60 wks PMA (both pre-term and full-term) who are orally feeding \geq 25% of at least 50% of their feeds who are on full enteral feeds with no more than 1LPM NC respiratory support. All infants will have a diagnostic VFSS scheduled.
- Exclusion criteria: Genetic or metabolic syndromes, grade III or greater, moderate to severe HIE, craniofacial, airway or foregut malformations or ENT or neuro surgeries. Infants who are exclusively breastfeeding are also excluded.
- Test-1: VFSS with concurrent or sequential pharyngo-esophageal manometry along with standard safety metrics. Esophageal and pharyngeal provocation induced

PROTOCOL TITLE: Neonatal Esophagus and Airway Interactions in Health and Disease: Mechanisms and Management of Infant Dysphagia

aerodigestive reflexes will be tested. Oral feeding challenge test is performed during manometry. The same procedures without VFSS will be repeated at Time-2 where feasible and relevant.

- Overall Study Endpoints: Primary endpoint is therapeutic success defined as full oral feeding without symptoms requiring intervention at 4 weeks (for outpatient studies and those still admitted at 4 weeks) or discharge, whichever is earlier. Secondary clinical end points include growth velocity and feeding outcomes at 1 year.
- Methods to overcome Potential Confounders: It is NICU standard to document in EPIC: i) Daily documentation of symptoms, medication use, feeding methods and duration, feeding volume and weight, ii) Weekly documentation of growth velocity (weight, length, head circumference).
- Removal and management of subject(s) from protocol: The investigator and/or the parent(s) have the right to withdraw from study at any time and opt for the standard of care. Parent(s) that withdraw their infants from the study therapy will be encouraged to continue to remain in the study for all follow up evaluations. Those who choose complete withdrawal from the study will be encouraged to follow the standard of care; wherein, response failures are followed until 1st birthday in the multidisciplinary developmental follow-up clinic.
- Intermediate outcome measures (up to 1 yr age): Acquisition of feeding and GI milestones during first year of life.

6.2 Describe:

- Manometry methods have been used concurrent with video, submental EMG, RIP, ECG, pulse-oximetry and nasal air flow to test basal and adaptive pharyngo-esophageal reflexes and sensory-motor characteristics of motility and to monitor safety. Concurrent synchronized video recordings will be performed to further validate symptoms based on objective definition of the esophageal reflexes. Documentation of symptom markers can be validated by integrating manometry with respiratory inductance plethysmography and video.
- Multimodal esophageal and pharyngeal sensory-motor testing protocols: We have developed and extensively used these protocols to measure sensory-motor characteristics of

PROTOCOL TITLE: Neonatal Esophagus and Airway Interactions in Health and Disease: Mechanisms and Management of Infant Dysphagia

reflexes, and these testing protocols will be performed as validated and reported

- The source records that will be used to collect data about subjects will be EPIC records, patient diary logs for symptoms, feeding process, medication compliance, physician visits and clinical data.

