2.0 Objectives

2.1 Purpose, Specific Aims or Objectives

- Our overall aims are to identify novel diagnostic aerodigestive targets, define effective therapeutic interventions, and advance the mechanistic basis of therapeutic outcomes. Infants with aerodigestive and feeding difficulties, who had VFSS undergo Manometry study to ascertain the mechanisms of normal or abnormal swallowing. Parent-preferred therapy is implemented. Changes in therapy modes are documented. Repeat manometry study is undertaken at time-2, which is 2-4 weeks after the initial study where feasible (this may happen in those with oral feeding failures).
- Based on the VFSS results evaluations, there are 2 possible scenarios: those with abnormal or normal results. Parent preferred therapeutic feeding (flow change, thickener change, no change) strategy is implemented and we will simply monitor the progress of the feeding efficiency till discharge or four weeks, whichever is earlier. There are 2 possible outcomes: feeding success, i.e., full oral feeds without symptom requiring intervention or feeding failure, i.e., those needing any tube feeding.
- We will review the motility characteristics of the successful and failure cases to identify the diagnostic markers.

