- Three references are attached below in this section that lend support to our investigations, difficulties with strict protocols and need for personalization and parent preferred pragmatic therapies. Complimentary protocols (feeding outcomes in dysphagia, mechanisms of dysphagia, outcomes in gastrostomy bound infants) will address the original study aims as well. Updated statistical procedures based on the advice of our statistician, [name], PhD, DSMB team, and our Program Project Group is shown below.

3.3 Updated statistical procedures:

- The design of the Patient Preferred Trial has been modified to a single arm observational study with patients who have not achieved PO at the time of study or PO with feeding difficulties, comparing VFSS and manometry vs VFSS only (the historical control) on feeding outcomes. The primary outcome is success rate at discharge. We will prospectively follow 60 infants who are not fully PO or PO and symptomatic at the time of study. Based on our Feeding Outcomes of Dysphagia Study (vs. historical control), the success rate at discharge is around 60%. With 60 patients enrolled, we will have 90% power to detect an absolute increase of 20% from 60% for those who do not have treatment informed by manometry (historical control) to 80% in those in the manometry informed group with two-sided type I error of 0.05. Achievement will be assessed by tracking feeding methods at discharge or 4 weeks whichever is earlier and then at 1 year.
- [name], Peng J, Moore R, Saavedra J, Shepherd E, Fernandez S, Erdman SH, DiLorenzo C. Impact of personalized feeding program in 100 NICU infants: pathophysiology-based approach for better outcomes. *J Pediatr Gastroenterol Nutr.* 2012 Jan;54(1):62-70.
- [name], Stoner E, Gupta A, Bates DG, Fernandez S, Di Lorenzo C, Linscheid T. Evaluation and management of neonatal dysphagia: impact of pharyngoesophageal motility studies and multidisciplinary feeding strategy. *J Pediatr Gastroenterol Nutr.* 2009 Feb;48(2):186-92
- [name], Khot T, Moore R, Malkar M, Gulati IK, Slaughter JL. Feeding Methods at Discharge Predict Long-Term Feeding and Neurodevelopmental Outcomes in Preterm Infants Referred for Gastrostomy Evaluation. *J Pediatr.* 2017 Feb;181:125-130

3.4 Scientific or scholarly background for, rationale for, and significance of the research based on the existing literature and how will it add to existing knowledge

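### Infants already in the success state can be enrolled, and the unadjusted comparison with historical controls ignores how many of them each group contains

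*Combined protocol and SAP*

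**What the plan says.** **Entry.** Section 6.1 describes both groups: "Study and control infants have oral feeding difficulties with symptoms requiring interventions/monitoring". Its oral-intake criterion is a floor with no ceiling: orally feeding at least 25% "of at least 50% of their feeds who are on full enteral feeds with no more than 1LPM NC respiratory support". Section 3.3 names fully oral infants as part of the sample: "We will prospectively follow 60 infants who are not fully PO or PO and symptomatic at the time of study". The design sentence in the same section gives the same mix: "patients who have not achieved PO at the time of study or PO with feeding difficulties".

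**Endpoint.** Section 6.1: "Primary endpoint is therapeutic success defined as full oral feeding without symptoms requiring intervention at 4 weeks", or at discharge if that comes first. Section 4.0 words it as "independent oral feeding without symptoms requiring intervention by 4 weeks or sooner". Section 2.1 sets against success "feeding failure, i.e., those needing any tube feeding". None of these asks for a change from the infant's state at entry, and none defines when a symptom requires intervention.

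**Analysis.** Section 9.2 analyses every consented infant who has both VFSS and manometry. Section 16.1 compares study infants with the historical controls by chi-squared or Fisher's test for categorical outcomes. Its only covariate model for feeding success concerns comorbidities. Under potential confounders, section 6.1 lists routine chart documentation and no adjustment. For the controls, section 3.3 states that "the success rate at discharge is around 60" per cent, and it plans 60 infants for 90% power against 80%.

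**The concern.** The entry description accepts symptoms that need intervention or only monitoring, whereas the success definition is concerned only with symptoms that need intervention. A fully oral infant under observation alone passes the first and already satisfies the second. Such an infant adds a success without any change in condition.

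In a randomised trial, chance would balance these infants between arms. Here the controls are historical and the test is unadjusted, so a difference in case mix at entry passes directly into the estimated effect of manometry. More of these infants in the study group would look like benefit; more among the controls would hide it. As planned, a reader of the results could not tell which had happened, because entry status under the endpoint rule is not derived for either group.

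**Working it through.** **1. The definitions side by side**

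| State at entry | Eligible? | Under the success rule | Counted if nothing changes |
|---|---|---|---|
| Not fully oral | Yes (3.3, 6.1) | Not met | Failure |
| Fully oral, symptoms requiring intervention | Yes (3.3, 6.1) | Not met | Neither success nor, under 2.1, failure |
| Fully oral, symptoms only monitored | Yes (3.3, with the 6.1 population description) | Met | Success |

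The third row is the overlap. The second row is a related gap: the two outcomes in section 2.1 do not cover it.

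**2. The plan's own figure**

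Inputs from section 3.3: 60% versus 80%, two-sided 0.05, 90% power. For one sample against a fixed 60%:

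n = [(1.96 × √(0.6 × 0.4) + 1.2816 × √(0.8 × 0.2)) / 0.2]² = 54.2

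With continuity correction: n/4 × [1 + √(1 + 2/(0.2n))]² = 59.1, rounded up to 60. The stated size is reproduced and is not in dispute. The matching exact rule at n = 60 is 44 or more successes, with an upper tail of 2.2% at 60% and power of 92.3% at 80%.

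**3. What an unequal share does when manometry has no effect**

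Let s and c be the shares already at the endpoint in the study and control groups, r the chance that such an infant is still a success at assessment, and q the success rate in all other infants, the same in both groups.

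- Control rate: c·r + (1 − c)·q = 0.60
- Study rate: s·r + (1 − s)·q
- Difference: (s − c)(r − q)

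The difference is zero when s = c and changes sign when c exceeds s. The documents give none of s, c or r, so every value below is an assumption. The last column is the exact chance of 44 or more of 60.

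| Assumptions | Study share s | Study rate | Chance of apparent benefit |
|---|---|---|---|
| Worst case: c = 0, r = 1, q = 0.60 | 10 / 20 / 30% | 64 / 68 / 72% | 8 / 23 / 47% |
| c = 0, r = 0.85, q = 0.60 | 10 / 20 / 30% | 62.5 / 65 / 67.5% | 5 / 11 / 21% |
| c = 20%, r = 1, q = (0.60 − 0.20)/0.80 = 0.50 | 20 / 30 / 40% | 60 / 65 / 70% | 2 / 11 / 34% |

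Each is to be read against the nominal 2.2%.

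**4. The test in section 16.1**

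That test has two samples, and the number of controls is not stated. Under the worst-case row, an assumed 60 controls give about 7 / 15 / 29% and an assumed 200 give about 8 / 20 / 40%. The fixed-60% figures are therefore upper values.

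**5. Cost of restricting to infants not at the endpoint on entry**

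With 60 enrolled and 10 / 20 / 30% already at the endpoint, 54 / 48 / 42 remain. Exact power for 60% versus 80% in those infants is about 89 / 85 / 80%.

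**The case against.** The overlap depends on one word after a slash, in a population description and not in the inclusion criteria. The plan does try to keep entry and endpoint apart: fully oral infants enter only if symptomatic, and all have a diagnostic need for VFSS. If a change of flow or thickener counts as an intervention, few infants may start in the success state. This stands as far as the number goes: the share is unknown and could be near zero. It does not remove the problem, because the term is undefined and sections 2.1 and 7.1 list no change as one of the parents' options.

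The same entry description also covers the controls. That stands too: with equal shares there is no false-positive inflation. But shared wording does not make the shares equal, and nothing in the plan measures or controls them.

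Three stronger readings are tempting, and the documents do not support them.

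- *These infants achieve the endpoint on day 0.* The endpoint is assessed at 4 weeks or discharge, and an infant in the success state at entry may have left it by then.
- *The study group holds more of them, so the result favours manometry.* No passage describes the controls' oral-feeding status at entry, or says that outpatients were left out of the control group.
- *The planned 20-point gain is diluted.* Section 3.3 states 60% and 80% for the whole enrolled population, in the same bullet that admits fully oral infants. Those rates may already include them.

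**Conclusion.** The concern holds in a limited form. The plan admits infants who are already in the success state, counts them as successes if nothing changes, and compares groups without regard to how many each contains. The comparison is biased only if the shares differ, in a direction that the documents do not fix.

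If they differ, the effect can be material: a 10-point excess in the study group moves the expected success rate by 2.5 to 5 points in the scenarios shown, and a 20-point excess by 5 to 10. The 47% figure is a worst case. It needs a 30% share in the study group, none among controls, every such infant remaining a success, and a fixed control rate. This is an inexpensive improvement worth making, and not evidence that the result is wrong.

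**What to change.** 1. Write one definition of symptoms requiring intervention, set by the study team, and use it at both entry and endpoint in both groups.
2. Apply the endpoint rule at baseline to every study and control infant, giving three classes: not fully oral; fully oral with symptoms requiring intervention; already meeting the endpoint. Report the classes by group.
3. Keep all infants in the study-versus-control comparison of success, but stratify by this status or adjust for it.
4. Report the comparison restricted to infants not meeting the endpoint at entry as a key sensitivity analysis. Making it the primary analysis is harder to justify: it loses precision, and the current version (10/2/20) is dated after the planned end of enrolment (7/20).
5. State how a fully oral infant with symptoms requiring intervention is classified at the endpoint, since section 2.1 leaves that case open.

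The cost is SAP wording, one derived baseline variable and some chart abstraction. Section 6.1 describes daily recording of feeding method and symptoms as NICU standard, so controls and outpatients are where extra abstraction is most likely. The restricted analysis has lower power, as shown in the last step of the working.

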16.0 Data Management* and Confidentiality

16.1 Data Analysis Plan

- Descriptive statistics will be reported as median (IQR), mean \pm SD or total number and percentage for demographics and clinical characteristics. For PPG vs FOD historical control comparisons, two-sample t-test or ANOVA will be used for the continuous variables and chi-squared or Fischer's exact tests will be used for the categorical variables, whichever is appropriate. Non-parametric method (e.g. Wilcoxon) might be used if the data is not normally distributed. Normality will be assessed using Shapiro-Wilks test and visually inspection of the data. For other Normal vs Abnormal VFSS and the effect of parent preferred therapy -flow modification or thickener use) comparisons, due to the nature of the repeated measure of the data, repeated measure ANOVA for continues measured variables and Generalized estimating equation (GEE) for categorical variables, to predict the likelihood of the specific response, will be used as to make the between group comparisons. Compound symmetry (CS) will be specified for the covariance structure of the repeated data. Bonferroni correction will be used to conserve the overall type I error at $\alpha=0.05$. To characterize the association between the disease comorbidities and feeding success, simple and multiple logistic regression analysis will be performed. Statistical Analysis Software, version 9.4 (SAS Institute Inc., Cary, NC, USA)

- 16.2 Data will be stored in RedCap and each subject will have a file which is kept in a secured locked location.

- 16.3 Data will be verified by at least two individuals on the study team

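### The primary endpoint contains an undefined symptom judgement with no stated assessor, criteria or masking in an open comparison with historical controls, which leaves room for differential classification and type I error inflation

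*Combined protocol and SAP*

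**What the plan says.** **Endpoint.** Section 6.1 (Overall Study Endpoints): "Primary endpoint is therapeutic success defined as full oral feeding without symptoms requiring intervention at 4 weeks", or at discharge if earlier. Section 4.1 uses the same symptom component: "independent oral feeding without symptoms requiring intervention by 4 weeks or sooner". No section lists the symptoms or interventions that count, or names an assessor.

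**Other descriptions of the same outcome.** Section 2.1 gives two possible outcomes. Success includes the symptom condition, but the alternative is "feeding failure, i.e., those needing any tube feeding". Section 3.3 (Updated statistical procedures) says "Achievement will be assessed by tracking feeding methods at discharge or 4 weeks whichever is earlier and then at 1 year" and does not mention symptoms. It also makes infants who are fully oral but symptomatic at entry eligible.

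**Comparison.** Study infants are prospective and consented. Controls are historical infants from the same center who had VFSS alone (6.1). Manometry results go to the parents, and for inpatients the chosen feeding approach goes to the medical team (7.1).

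**Data.** Symptoms and feeding method are charted daily in EPIC as NICU standard (6.1). For subjects, the sources are EPIC and diary logs that cover symptoms (6.2). No diary is described for controls. The one check is in 16.3: "Data will be verified by at least two individuals on the study team". Masking and independent classification are not mentioned.

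**Analysis.** Section 3.3 gives 90% power with 60 infants for 60% against 80%, two-sided 0.05. Section 16.1 names chi-squared or Fisher tests for the comparison with historical controls.

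**The concern.** Full oral feeding is close to a recorded fact. Whether a fully oral infant's symptoms call for intervention is not. That call decides the result for any infant who was already fully oral and symptomatic at entry and stays fully oral.

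The primary hypothesis (2.2) is directional, group is known, and nothing in the plan holds the call to one standard in both groups. Two routes to a differential call are open:

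- The endpoint wording allows it. A fully oral, symptomatic infant fails the success definition in 6.1, does not meet the failure definition in 2.1, and would pass on feeding method alone as in 3.3.
- The sources allow it. Diary symptoms may be available for study infants and not for controls. This could push the result either way, since more symptom information can also mean more failures found.

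If borderline infants are called more favourably in the study group, or less favourably among controls, the primary comparison is biased and its nominal 5% error is not kept.

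**Working it through.** **Inputs.** From 3.3: n = 60, p0 = 0.60, p1 = 0.80, two-sided 0.05. From 16.1: chi-squared or Fisher test. Not given, so assumed: number of controls m (60, 100, 200), true control rate 60%, and number k of non-successes called as successes.

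**1. The plan's own power.** One-sample normal approximation with continuity correction:

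Φ{[(p1 − p0) − 1/(2n) − 1.96√(p0(1 − p0)/n)] / √(p1(1 − p1)/n)}
= Φ{[0.20 − 0.0083 − 1.96 × 0.0632] / 0.0516} = Φ(1.31) = 90.5%.

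The exact binomial gives 92.3%. The stated 90% is therefore reproduced as a test against a fixed 60%. A two-sample calculation gives 67.0%, 75.9% and 84.1% with 60, 100 and 200 controls. Because 3.3 and 16.1 imply different tests, both are used below.

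**2. Fixed 60%.** With X ~ Bin(60, 0.6), 44/60 is significant (p = 0.035) and 43/60 is not (p = 0.066). With k favourable calls the upper-tail error is P(X ≥ 44 − k):

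- k = 0: P(X ≥ 44) = 2.2%
- k = 3 (3/60 = 5 points): P(X ≥ 41) = 11.7%
- k = 6 (10 points): P(X ≥ 38) = 34.9%

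**3. Planned two-sample tests.** Let a ~ Bin(60, 0.6) and b ~ Bin(m, 0.6). The error is the total probability of pairs (a, b) for which the test on (a + k)/60 against b/m rejects in favour of the study group. The chi-squared test uses

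z = (a/60 − b/m) / √(p̄(1 − p̄)(1/60 + 1/m)), where p̄ is the pooled rate.

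| Controls, test | k = 0 | k = 3 | k = 6 |
|---|---|---|---|
| 60, chi-squared | 2.6% | 8.5% | 21.8% |
| 60, Fisher | 1.6% | 5.9% | 16.4% |
| 100, chi-squared | 2.5% | 9.4% | 25.1% |
| 100, Fisher | 2.3% | 8.7% | 23.6% |
| 200, chi-squared | 2.5% | 10.6% | 29.6% |
| 200, Fisher | 2.0% | 9.2% | 27.1% |

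**4. Calls needed from the expected null result, 0.6 × 60 = 36 successes.**

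- Fixed 60%: 44 − 36 = 8 calls, a third of the 24 failures.
- Planned tests, controls observed at exactly 60%: 45 to 47 successes are needed, so 9 to 11 calls. Example with 60 controls: 46/60 against 36/60 has p̄ = 82/120 = 0.683 and z = 0.1667/0.0849 = 1.96, p = 0.0497.
- Calls in both groups, 60 controls: six each way gives 42/60 against 30/60, chi-squared p = 0.025, Fisher p = 0.040.

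**5. Plausibility of k.** The share of failures that turn on symptoms is unknown. Against a fixed 60%, if 25% do and half of those are called favourably, the apparent rate is 0.60 + 0.40 × 0.25 × 0.5 = 0.65 and the error 11.0%. If 50% do and 20% are called favourably, the rate is 0.60 + 0.40 × 0.5 × 0.2 = 0.64 and the error 8.3%.

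**The case against.** **Much of the outcome is a recorded fact.** Tube feeding is objective, symptoms are charted daily as routine care, and on the wording of 2.1 and 3.3 few infants may turn on symptoms at all. This stands as a limit on the size of the bias. It does not remove the bias, because 4.1 and 6.1 put symptoms in the primary endpoint and fully oral symptomatic infants are eligible.

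**Who makes the call is not stated.** A reader might infer that the unmasked study team classifies its own infants and the controls. The protocol does not say so. It names study-team members only as data verifiers, and it is silent on how or by whom the historical controls' symptoms were classified. What can be said is that assessor, criteria and masking are unspecified for both groups.

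**The team's expectation.** A reader might take 80% as what the team expects. Section 3.3 gives it as a detectable difference for power, and 2.2 states superiority without a figure. Only the direction of the hypothesis can be relied on.

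**The fixed-rate figures overstate the inflation.** For the tests named in 16.1 this is correct. In every two-sample case examined, the error after three or six calls is below 11.7% or 34.9%.

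**Two people already verify the data.** True, but verifying entries is not the same as classifying the endpoint independently without knowledge of group.

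**Conclusion.** The concern holds in a limited form. The primary endpoint includes a judgement with no stated assessor, criteria or masking. The comparison is open, a symptom source is named for one group only, and the endpoint descriptions in 2.1, 3.3, 4.1 and 6.1 do not agree on the fully oral, symptomatic infant.

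The size, under the planned tests, is an upper-tail error that rises from about 2% to 6-11% with three favourable study-group calls and to 16-30% with six. Against a fixed 60%, the basis that reproduces the stated power, it goes from 2.2% to 11.7% and 34.9%.

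It would be tempting to conclude that a handful of calls can manufacture a significant result. That is so only near the boundary, where one call turns 43/60 into 44/60. From the expected null result, 8 calls are needed against a fixed 60% and 9 to 11 under the planned tests.

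The figures rest on assumed numbers of controls and of borderline infants and on a true rate of 60% in both groups. The protocol shows that differential calling is possible, not that it occurs. The change should be made, because it is cheap and protects the primary comparison.

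**What to change.** 1. Reconcile 2.1, 3.3, 4.1 and 6.1 on whether symptoms are part of the primary endpoint, so that every infant is either a success or a failure.
2. If symptoms stay in, write one set of criteria for the symptom component and apply it to both groups. Masked readers without criteria would still be guessing. The content is for the investigators to set.
3. Amend 6.1 and 16.3 so that the two verifiers already planned each classify success or failure independently, for study and control infants alike. Use one form drawn from the same chart source in both groups, with no diary data used for one group only. Remove group, dates and manometry result. Keep any feeding change that the criteria count as an intervention, stated in neutral terms, since the reader needs it to judge the endpoint.
4. Settle disagreements before unmasking and report agreement (kappa) by group.
5. Add a sensitivity analysis on any tube feeding (yes/no) at the same time point.

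**Cost.** A form in REDCap and time to prepare the redacted extracts, ideally by someone other than the two readers. No new infants, visits or change in care. Masking will be partial, because bedside charting is open and verifiers may recognise some infants, so the bias is reduced and not removed.

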1.0 Study Summary

Study Title	Neonatal Esophagus and Airway Interactions in Health and Disease: Mechanisms and Management of Infant Dysphagia
Study Design	Single arm observational study
Primary Objective	Our overall aims are to identify novel diagnostic aerodigestive targets, define effective therapeutic interventions, and advance the mechanistic basis of therapeutic outcomes-i.e., full oral feedings.
Secondary Objective(s)	
 1) Examine the differences in outcomes among preterm born vs. full term born 2) Examine the differences in outcomes among those with normal versus abnormal VFSS
Research Intervention(s)/Investigational Agent(s)	Providing esophageal manometry concurrent with video fluoroscopy swallow study (VFSS) in order to determine sensory-motor dysphagic mechanisms which will better inform treatment options
IND/IDE #	N/A

PROTOCOL TITLE: Neonatal Esophagus and Airway Interactions in Health and Disease: Mechanisms and Management of Infant Dysphagia

Study Population	
All infants will have a diagnostic VFSS scheduled.
 
Inclusions: Infants with feeding-related aerodigestive symptoms who are \leq 60 weeks PMA (both pre-term and full-term) who are orally feeding $\geq 25\%$ of at least 50% of their feeds who are on full enteral feeds with no more than 1LPM NC respiratory support.
 
Exclusions: Genetic or metabolic syndromes, IVH grade III or greater, moderate to severe HIE, craniofacial, airway or foregut malformations or ENT or neuro surgeries. Infants who are exclusively breastfeeding are also excluded.

Sample Size	60
Study Duration for individual participants	Up to 4 weeks (initial manometry study with diagnostic VFSS, repeat manometry at 4-6 weeks as relevant), will follow feeding outcomes and growth and developmental outcomes for 1 year
Study Specific Abbreviations/ Definitions	
VFSS video-fluoroscopy swallow study
 
LP laryngeal penetration
 
LA laryngeal aspiration

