7.0 Sharing of Results with Subjects*

- 7.1 Manometry results are shared with the parents at the time of the study. Parents decide on their preferred feeding approach (flow change, thickener change, no change) and if the patient is inpatient, this is shared with the medical team.

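### The primary endpoint is read at discharge for some infants and at 4 weeks for others, so a difference from the historical controls in setting mix or discharge timing can shift the comparison in either direction

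*Combined protocol and SAP*

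**What the plan says.** Section 6.1 defines therapeutic success as full oral feeding without symptoms that require intervention, assessed "at 4 weeks (for outpatient studies and those still admitted at 4 weeks) or discharge, whichever is earlier". Section 2.1 says the team will "monitor the progress of the feeding efficiency till discharge or four weeks, whichever is earlier", with no separate rule for outpatients, and counts any need for tube feeding as failure.

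Section 3.3 gives two read times: one sentence puts the primary outcome at discharge, another at the earlier of discharge and 4 weeks, and then at 1 year. Section 4.1 allows success at any time up to 4 weeks. None of these defines the day from which the endpoint's 4 weeks run.

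The benchmark comes from historical controls: "the success rate at discharge is around 60" per cent (section 3.3). The documents do not give the number of controls, their inpatient/outpatient split, or whether their outcome was capped at 4 weeks.

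Section 16.1 compares the groups on categorical outcomes by chi-squared or Fisher's exact test. The only regression planned for feeding success concerns comorbidities. Length of stay is collected (section 6.3) but is not given a role in the primary comparison. The parents' chosen approach is disclosed for inpatients: "if the patient is inpatient, this is shared with the medical team" (section 7.1). For the longer term, the Study Summary says the study "will follow feeding outcomes and growth and developmental outcomes for 1 year".

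**The concern.** Under section 6.1, two infants with the same feeding course can be scored differently. Take an inpatient sent home on a tube on day 10 and an outpatient on a tube that same day, both tube-free by day 28. The inpatient is a primary-endpoint failure and the outpatient a success.

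Within one group scored by one rule, this is only a feature of the endpoint. It becomes a source of bias when two groups are compared that may differ in the share of outpatients, or in how early infants are discharged. Here the comparator is historical and study enrolment runs from 2/16 to 7/20, so nothing in the design balances either factor. The planned test does not adjust for them. A difference in setting or discharge practice could then be read as an effect of manometry and parent choice, or could hide a real one.

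**Working it through.** **Inputs from the documents.** Study group n = 60, benchmark 60%, target 80%, two-sided 0.05 (section 3.3); chi-squared or Fisher's exact test (section 16.1). Not given: number of controls, setting mix in either group, discharge-time distribution, success by setting.

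**1. The plan's own figure.** Section 3.3 states: "With 60 patients enrolled", "we will have 90% power to detect an absolute increase of 20" points. A one-sample test against a fixed 60%, with continuity correction, gives

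z = (0.20·√60 − 1/(2√60) − 1.96·√(0.6·0.4)) / √(0.8·0.2) = (1.549 − 0.065 − 0.960)/0.4 = 1.31, so power is 90.5%.

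The exact binomial rule (at least 44 of 60 successes) has upper-tail error 2.2% and power 92.3%. The 90% therefore reproduces if 60% is a known constant. As a two-sample test it needs about 600 controls (90.0%); with 60 controls, power is 67.0%. The power statement is not in dispute here, but the illustrations below must use the two-sample test that section 16.1 plans.

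**2. Read times side by side.**

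| Place | When success is read |
|---|---|
| 2.1 | Earlier of discharge and 4 weeks |
| 3.3, primary outcome | Discharge |
| 3.3, tracking | Earlier of discharge and 4 weeks |
| 3.3, benchmark | Discharge, no cap stated |
| 4.1 | Any time up to 4 weeks |
| 6.1 | Discharge if before 4 weeks; 4 weeks for outpatients and those still admitted |

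These are not one rule. The day-10 inpatient above fails under 6.1 but could count as a success under 4.1.

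**3. Setting mix (assumed inputs).** Let outpatients succeed at 80% and inpatients at 60%, with no effect of the strategy. With outpatient share f, the pooled rate is 0.60(1 − f) + 0.80f: 65% at f = 0.25 and 68% at f = 0.40. The table gives the probability that an uncorrected two-sample chi-squared test at two-sided 0.05 favours the study group, summed exactly over both binomials, for f = 0.25 and f = 0.40.

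| Controls | No outpatient controls (60%) | Half the study share (62.5%, 64%) |
|---|---|---|
| 60 | 8.2%, 14.7% | 4.7%, 6.8% |
| 120 | 9.2%, 17.7% | 5.0%, 7.5% |
| 300 | 10.5%, 20.8% | 5.3%, 8.1% |
| 600 | 10.8%, 21.9% | 5.3%, 8.4% |

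With equal mixes the probability is 2.3-2.6%, which is nominal. Fisher's exact test is more conservative: with no outpatient controls, 6-11% for 60 controls and 8-16% for 120. If the rates or the mix were reversed, the bias would run against the strategy.

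**4. Discharge timing (assumed inputs).** Suppose 60% are fully oral by day 28 at a constant rate, so S(t) = 1 − 0.4^(t/28), giving S(7) = 20.5% and S(14) = 36.8%. If a fraction q of infants still tube-fed on day t go home that day and the rest are followed to day 28, recorded success is S(t) + (1 − q)(0.60 − S(t)).

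| Day t | q = 0.2 | q = 0.3 |
|---|---|---|
| 14 | 55.4% | 53.0% |
| 7 | 52.1% | 48.1% |

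The feeding process is unchanged, yet recorded success falls from 60% to about 48-55%. If this happens more in the study group it works against the strategy: under the exact one-sample rule, lowering a true 80% to 75% cuts power from 92.3% to 68.0%. If it happens more among controls, it favours the strategy.

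**The case against.** Leaving hospital on a tube is a meaningful failure under a hypothesis about preventing long-term tubes, so reading inpatients at discharge is a defensible choice. If the controls were scored by the same rule, with a similar mix and similar discharge timing, the bias would be small or absent. Both points stand. The documents do not say that the controls were scored this way, and the benchmark is described only as a rate at discharge.

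It is also fair that every rate by setting and every discharge time above is assumed. Several stronger readings are tempting but unsupported:

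- A reader might infer that most inpatients are scored at discharge. The share discharged before 4 weeks is not given.
- A reader might infer that the care team times discharge according to feeding status or the chosen strategy. Section 7.1 says only that the choice is shared with the team.
- A reader might test the 65-68% pooled rates against a fixed 60% and quote a false-positive risk of 11-23%. That uses a one-sample test, which section 16.1 does not plan, and assumes no outpatients among controls.
- A reader might infer that the bias favours manometry. The mix and timing mechanisms can pull in opposite directions, and the net sign is unknown.
- A reader might infer that no common-time reading exists. Feeding at 1 year is a named secondary endpoint. It does not, however, repair the primary comparison.

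**Conclusion.** The concern holds as a possible bias of unknown size and direction. The primary endpoint has a read time that depends on setting and discharge date, the plan's statements of that read time differ, the benchmark's read rule and setting mix are not stated, and the planned test adjusts for neither factor.

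On the assumed rates of 80% and 60%, with 25-40% outpatients in the study group and none among controls, the chi-squared test declares a false benefit in about 8-15% of trials with 60 controls and 11-22% with 600. This falls to about 5-8% if controls have half the study group's outpatient share, and to nominal if the mixes match. Early discharge on a tube lowers recorded success, for example from 60% to 48-55%. These figures show that modest differences between groups matter at n = 60; they do not estimate the bias in this study.

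**What to change.** 1. Reconcile sections 2.1, 3.3, 4.1 and 6.1 to one read-time rule with a defined day zero, and score the historical controls by that same rule.
2. Stratify the primary comparison by setting at VFSS (inpatient or outpatient), using a Mantel-Haenszel risk difference, and show both strata. If the controls include no outpatients, restrict the controlled comparison to inpatients and report outpatients descriptively.
3. Stratification deals with mix but not with discharge timing. So add a supportive analysis of feeding status at day 28 in all study infants, and in controls where it is charted. Report by group the number read before day 28, the read day, and the number discharged on a tube.

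The cost is changed analysis wording, some extra chart abstraction and slightly lower precision. Study infants are already followed for a year. Day-28 status may be incomplete in controls, which is why that analysis is supportive only.
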